3.1 Study Rationale

The purpose of this protocol is to assess pharmacokinetics (PK), safety, and efficacy of EBR and GZR in a population of pediatric HCV-infected participants aged 3 years up to 18 years. These data will be used to support dosing recommendations in the pediatric population. EBR/GZR with and without ribavirin (RBV) has been developed and approved for adults with chronic hepatitis C genotype (GT) 1 or 4. Diverse adult populations have been studied including those with cirrhosis, human immunodeficiency virus type 1 (HIV-1) co-infection, end stage renal disease, and prior treatment failure. Efficacy rates exceed 90% regardless of these underlying co-morbidities or patient characteristics.

Historically, children treated for HCV have had similar response rates as adults when given a similar regimen at the appropriate dose. The adult EBR/GZR PK model is highly predictive of clinical response (safety and efficacy in adults). Therefore pediatric patients are anticipated to have a similar safety and efficacy profile when given doses that achieve a similar exposure as that seen in adult patients. The intensive PK obtained at Treatment Week (TW) 4 will be used to update the adult population PK model to support dosing recommendations in the pediatric population.

3.2 Background

Refer to the Investigator's Brochure (IB)/approved labeling for detailed background information including preclinical and clinical trial data for EBR/GZR.

3.2.1 Pharmaceutical and Therapeutic Background

MK-5172 is comprised of the following 2 direct-acting antiviral (DAA) HCV agents:

- EBR (elbasvir, MK-8742) is an HCV NS5A inhibitor.
- GZR (grazoprevir, MK-5172) is an HCV NS3/4A protease inhibitor.

Each MK-5172 FDC tablet contains EBR (50 mg) and GZR (100 mg) and is administered once daily (QD). Participants in Mini Age Cohort 1 (oldest Age Cohort) will receive the FDC tablet. This will also apply to participants in Expanded Age Cohort 1 if it is determined by PK analysis that Expanded Age Cohort 1 will also receive the adult FDC dose. The two younger age cohorts will receive EBR pediatric formulation and GZR pediatric formulation. See Section 7.1 for a description and dosing instructions of the EBR/GZR pediatric formulation.

3.2.1.1 Overview

Children with chronic hepatitis C are vulnerable to the same long-term health consequences as adults, including progressive liver damage, cirrhosis, and hepatocellular carcinoma (HCC). Developing an age appropriate, all-oral, well tolerated, short duration treatment regimen for HCV infected children is highly desirable for a population that is currently restricted to the current pediatric standard of care, pegylated-interferon with RBV (PR). In contrast to the current safe and convenient therapies available to adults, PR most commonly requires 48 weeks of therapy, with weekly injections. The therapy has many adverse events (AEs), including flu-like symptoms, anemia, and impairment of growth, while achieving a sustained virologic response (SVR) of only ~50%.

Epidemiology of Chronic Hepatitis C

Worldwide it is estimated that 3 to 4 million people are newly infected with HCV annually and 170 million are chronically infected [Hanafiah, K. M., et al 2013]. For those who are chronically infected, there is a lifetime risk of developing progressive liver damage, cirrhosis, and liver cancer. In the United States (US), approximately 2.2 to 3.2 million persons are estimated to have chronic HCV infection based on a national survey of the civilian, non-institutionalized population [Denniston, M. M., et al 2014].

Of the patients infected with HCV, many are children. Seroprevalence data for children aged 1 to 15 years in the US and in Western Europe are 0.6% and 0.8-1.3%, respectively. The prevalence is similar to the 20-30 year old population in each of these regions [Hanafiah, K. M., et al 2013]. Most studies that have investigated the seroprevalence of HCV in childhood fail to investigate whether HCV antibody-positive children are also HCV viremic.

Extrapolating from adult studies, it is estimated that approximately 50-80% of those with positive HCV antibody are chronically infected and viremic [Aach, R. D., et al 2000] [Vogt, M., et al 1999].

Modes of Transmission of HCV in Pediatrics: Vertical transmission of HCV infection is the most common route of acquiring HCV infection in infants and children. In the US, there are approximately 7500 new cases per year from vertical transmission [Mack, C. L., et al 2012]. Mother to child transmission among HCV mono-infected women is approximately 5%. Although the risk is low for an individual, HCV infection is common, and thus accounting for a significant number of new infections in newborns annually. Among HIV-1/HCV co-infected women, vertical transmission can be as high as 25%. Other modes of transmission in pediatrics, include household contacts and most importantly, especially among adolescents, acquisition due to high risk behaviors such as injection drug use, tattoos, and piercings. For children younger than the age of 3 years, results from a prospective study following a birth cohort have shown that 17% had spontaneous viral clearance by age 2 and 24% had clearance by age 3 [England, K., et al 2005] [Narkewicz, M. R., et al 2007]. It is because of this early predilection for spontaneous clearance that treatment trials for children with chronic HCV do not include the age group from birth to age 3 years.

Therapy for Chronic Hepatitis C

The therapeutic goal of treatment of hepatitis C is the eradication of the virus with a halt in the progression of liver damage. Similarities in the treatment response characteristics of

chronic HCV in adult and pediatric populations support the premise that therapeutic advances demonstrated in adults will likely be applicable to children. Historically, children have benefited from a similar approach to treatment of chronic HCV as adults [Kelly, D. A., et al 2011] [Wirth, S., et al 2010]. As of 2017, high efficacy was observed in a Phase II trial and supported approval in children aged 12 to 18 of an all-oral DAA regimen of sofosbuvir/ledipasvir [Balistreri, W. F., et al 2016]. The observed efficacy in the pediatric population in this study was similar to that seen among adults treated with the same regimen. Children should benefit from the new generation of HCV treatments that are all oral, safe, and effective. These advances are substantial improvements compared to the current standard of care for children, which is 24 to 48 weeks of PR.

It is anticipated that EBR/GZR dosed to provide the same PK exposures achieved in the adult population will be an effective and safe pediatric HCV therapy for GT1 and GT4 infection, as indicated in adults.

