5.4.2.1.1 Measurement of HCV RNA

HCV RNA plasma levels will be measured using the Roche COBAS[®] AmpliPrep/COBAS[®] TaqMan[®] HCV Test, v2.0 on blood samples drawn from each participant at various time points prior to, during, and after dosing, as indicated in the SoA (Section 2).

They are also used to identify participants who meet HCV virologic failure criteria. HCV RNA levels are described as detailed in [Table 3](#).

Table 3 Nomenclature for Describing HCV RNA Levels

Abbreviation	Definition	HCV RNA Level
TND	Target not detected	HCV RNA not detected
TD(u)	Target detected but unquantifiable	HCV RNA <LLOQ
TD(q)	Target detected, quantifiable	HCV RNA ≥LLOQ

Definition of Efficacy Endpoints

Efficacy will be defined at different timepoints during the trial. Specific endpoints are:

- **SVR₁₂**: Participant has HCV RNA <LLOQ (either TD[u] or TND) 12 weeks after the end of all study therapy.
- **SVR₂₄**: Participant has HCV RNA <LLOQ (either TD[u] or TND) 24 weeks after the end of all study therapy.

Definition of Virologic Failure

Lack of efficacy at different timepoints in the trial will be categorized as:

- **Non-response**: Participant has HCV RNA detected at end of treatment without HCV RNA <LLOQ having been achieved while on treatment (note that breakthrough is captured below).
- **Rebound**: Participant has a rebound defined as $>1 \log_{10}$ IU/mL increase in HCV RNA from nadir while on treatment and confirmed from a separate blood draw within 2 weeks.
- **Virologic breakthrough**: Participant has a confirmed HCV RNA \geq LLOQ (TD[q]) after being <LLOQ previously while on treatment. Confirmation is defined as an HCV RNA \geq LLOQ from a separate blood draw repeated within 2 weeks.
- **Relapse**: Participant has a confirmed HCV RNA \geq LLOQ (TD[q]) following end of all study therapy, after becoming undetectable (TND) at end of treatment. Confirmation is defined as an HCV RNA \geq LLOQ from a separate blood draw repeated within 2 weeks.

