5.4.2.1.2 Viral Resistance Measurements

In this trial, RASs are defined as specific genetic substitutions that generate viral proteins that maintain function, but have reduced susceptibility to a DAA. As the presence of certain HCV RASs can lead to treatment failure, they are one of the most important considerations when treating with a DAA. Those genetic substitutions that impact efficacy outcomes may be present at baseline (ie, prior to therapy), or they may be treatment-emergent (ie, not detected at baseline, but which emerge and are selected over the course of therapy).

Blood samples for viral resistance assays are collected at:

- **Screening**: Testing will be done to assess for the presence of NS5A and NS3 RASs that have been associated with reduced efficacy for NS5A compounds (eg, ledipasvir, daclatasvir, EBR) or protease inhibitors (eg, simeprevir, boceprevir, telaprevir, GZR). In GT1a-infected participants, presence of NS5A RAS at amino acid position 28, 30, 31, and/or 93 will be used for enrollment criteria as outlined in inclusion/exclusion.
- **Virologic failure and/or selected follow-up visits**: To better understand the emergence and natural history of RASs in association with virologic failure, samples will be obtained at virologic failure confirmation visits, Follow-up Week (FW) 4, FW12, and FW24. RASs will be assessed for any participant who has detectable virus above 1000 IU/mL and has met an HCV virologic failure criteria. Blood samples for resistance testing are also collected at all visits following confirmation of virologic failure to the end

of the trial. To limit the risk of RASs, participants are not allowed to have monotherapy with EBR or GZR in this protocol.

Participants who have met virologic failure criteria, will be offered follow-up in a 3-year long-term follow-up protocol, MK-5172 Protocol 017, to determine the persistence of RASs and to determine time course of reversion to wild-type.

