11. The participant is currently participating or has participated in a study with an investigational compound within 30 days of signing informed consent/assent and is not willing to refrain from participating in another such study through 24 weeks after the study treatment period (FW24).

Diagnostic assessments

12. The participant has exclusionary laboratory values at the screening visit as listed in [Table 4](#) below.

NOTE: If any of the laboratory exclusion criteria below in [Table 4](#) are met, the site may have the abnormal value retested one time.

Table 4 Laboratory Exclusion Criteria

Laboratory Assessment	Exclusionary Values
Creatinine clearance (eGFR) ^a	<50 mL/min/1.73 m ²
Hemoglobin	<10 g/dL
Platelets	<100 × 10 ³ /μL
Serum Albumin	<3.0 g/dL
INR	>1.7 (unless participant has a stable INR on an anticoagulant regimen)
ALT	>10 × ULN
AST	>10 × ULN

ALT = alanine aminotransferase; AST = aspartate aminotransferase; eGFR = estimated glomerular filtration rate; INR = international normalized ratio; ULN = upper limit of normal

^a Creatinine clearance will be evaluated as eGFR based on the modification of diet in renal disease equation:

$$\text{eGFR (mL/min/1.73 m}^2\text{)} = 175 \times (\text{Scr, std})^{1.154} \times (\text{Age})^{-0.203} \times (0.742 \text{ if female}) \times (1.212 \text{ if black})$$

Scr, std: serum creatinine measured with a standardized assay

Other Exclusions

13. The participant has significant emotional problems or a clinically significant psychiatric disorder that may interfere with participant treatment, assessment, or compliance with the protocol.

14. The participant has clinically relevant drug or alcohol abuse within 12 months of screening that may interfere with participant treatment, assessment, or compliance with the protocol.

15. Is or has an immediate family member (eg, spouse, parent/legal guardian, sibling or child) who is investigational site or sponsor staff directly involved with this study.

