Antihypertensives	Angiotensin-converting enzyme inhibitors or angiotensin receptor blockers: enalapril, captopril, lisinopril, ramipril, valsartan, losartan, telmisartan Beta blockers: atenolol, metoprolol, propranolol (for other beta blockers, please consult with the Sponsor) Calcium-channel blockers: amlodipine, diltiazem, verapamil (for other calcium-channel blockers, please consult with the Sponsor) Hydralazine, clonidine, minoxidil, isosorbide nitrates
Anemia	Erythropoietin
Diuretics	Hydrochlorothiazide, furosemide, spironolactone, triamterene
Opiate substitution therapy	Buprenorphine/naloxone, methadone Note: Participants in the Mini Age Cohorts are prohibited from taking methadone
Immunosuppressants	Prednisone, daily doses <10 mg or a short course lasting <2 weeks for higher doses.

Given that the lists above are not comprehensive, the investigator should use his/her medical judgment when a participant presents with a medication not on the list and consult with the Sponsor.

Concomitant medications and therapies discontinued during the dosing period may be restarted 2 weeks after the last dose of study drug is administered and may continue during the follow-up period.

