9.2 Efficacy Assessments

9.2.1 HCV RNA Measurements

Specimens must be obtained from all participants for the following HCV efficacy measurements:

- HCV GT on baseline sample (for trial entry) using the Food and Drug Administration (FDA) approved Abbott HCV Real Time Genotype II assay which detects HCV GT 1a, 1b, 2, 3, 4, 5, and 6 through the use of GT-specific fluorescent-labeled oligonucleotide probes in a real-time reverse transcription polymerase chain reaction (RT-PCR) assay. The RT-PCR reaction uses 3 sets of HCV specific amplification primers targeting the 5' untranslated region (for all GTs) and NS5B regions from GT1a and 1b. The assay has accuracy of >96% for GT1, 1a, 1b, 2, 3 and 5, 89% for GT5 and 83% for GT6 with 100% specificity in HCV serologically negative plasma samples. Phylogenetic analyses will be performed using sequences for NS3, NS5A, and NS5B regions to ensure accurate assignment of sample GT/subtype.
- HCV RNA plasma levels at various time points per the SoA (Section 2). HCV RNA in plasma will be measured using a COBAS® AmpliPrep/COBAS® Taqman® HCV Test, v2.0® assay with a LLOQ of 15 IU/mL. Results from the sample collected at the screening visit are used to determine eligibility. Samples collected at other time points, after Day 1, are used for efficacy analyses and to identify participants who meet virologic failure criteria. Leftover plasma may be used for viral resistance testing if needed.

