10.6.5.3 Viral Resistance Measurements

Viral resistance testing will focus on the entire NS3/4A and NS5A regions for all participants and for those who meet the virologic failure criteria (see Section 5.4.2.1.1).

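### Relapse is defined without a reinfection category or a strain comparison, so a new infection during follow-up would be reported as relapse and as failure in the supportive SVR12 analysis

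*Combined protocol and SAP*

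**What the plan says.** **Failure categories.** Section 5.4.2.1.1 defines non-response, rebound, breakthrough and relapse, and Section 10.6.3 summarises the same four. Relapse is confirmed HCV RNA at or above LLOQ "following end of all study therapy, after becoming undetectable (TND) at end of treatment". Confirmation is a second HCV RNA result "from a separate blood draw repeated within 2 weeks".

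**Supportive SVR12.** Under Section 10.5.2 the mFAS drops participants who discontinue the study for reasons unrelated to the regimen. Under Section 10.6.3 the TRD=F approach counts anyone with documented virologic failure, on treatment or in follow-up, as a failure.

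**Resistance.** Section 5.4.2.1.2 describes treatment-emergent substitutions as those "not detected at baseline, but which emerge and are selected over the course of therapy". After failure, RASs are assessed only if HCV RNA is above 1000 IU/mL and a failure criterion is met. Section 10.6.5.3 plans NS3/4A and NS5A testing "for all participants and for those who meet the virologic failure criteria". Section 9.2.1, in its item on the baseline genotype sample, adds: "Phylogenetic analyses will be performed using sequences for NS3, NS5A, and NS5B regions to ensure accurate assignment of sample GT/subtype".

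**Exposure.** Section 3.2.1.1 names vertical transmission as the commonest route in children. Among the other routes it lists "most importantly, especially among adolescents, acquisition due to high risk behaviors such as injection drug use, tattoos, and piercings". Exclusion criterion 14 bars "clinically relevant drug or alcohol abuse within 12 months of screening that may interfere with participant treatment" or that may interfere with assessment or compliance. Table 7 allows opiate substitution ("Buprenorphine/naloxone, methadone"), with methadone barred in the Mini Age Cohorts.

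**The concern.** A repeat RNA draw shows that virus is present, not which virus it is. A child who clears the infection, is TND at end of treatment and then acquires a different strain meets the relapse definition in full. The trial would report a failure of EBR/GZR where the drug had worked.

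Three outputs are exposed: the descriptive relapse rate, the supportive SVR12 (and SVR24), and the exploratory summary of emergent NS3/NS5A RASs. The last is open to this because GT1a participants enter only without NS5A RASs at positions 28, 30, 31 and 93. A new strain carrying one of these would show a substitution absent at baseline, and no step asks whether it arose in the participant's own virus.

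The numbers are small enough for one case to show. At the plan's expected response of about 95%, failures of all kinds, including dropouts under M=F, would number about 22 × 0.05 = 1.1 in Age Cohort 1 and 56 × 0.05 = 2.8 overall.

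**Working it through.** **1. Trace one reinfected participant through the rules.** Suppose an adolescent is TND at end of treatment, acquires a new strain, has confirmed quantifiable RNA at FW12 and stays in the study.

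- Failure category: relapse is the only one that fits.
- FAS, M=F: SVR12 not achieved, so failure.
- mFAS: not removed, because removal is tied to study discontinuation.
- TRD=F: failure, because virologic failure is documented in follow-up.
- RAS summary: sequenced only if RNA is above 1000 IU/mL. A substitution absent at baseline could then be counted as emergent, since no strain check intervenes.

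The Schedule of Activities places HCV genotype determination at screening only, so no later genotype result would flag a change of strain.

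**2. Reproduce the plan's figures.** Two-sided 95% Clopper-Pearson, N = 22 (Table 13). The lower limit is the 0.025 quantile of Beta(x, n − x + 1). The upper limit is the 0.975 quantile of Beta(x + 1, n − x), or 1 when x = n.

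- 22/22: lower = 0.025^(1/22) = 0.846, giving 100% (84.6, 100.0).
- 21/22: lower = 0.025 quantile of Beta(21, 2) = 0.772; upper = 0.975^(1/22) = 0.999, giving 95.5% (77.2, 99.9).

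Both match Table 13, as do its other 14 rows.

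**3. One reinfection by FW12 among 22 otherwise cured adolescents, supportive analysis.**

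| Rule | Result | 95% CI |
|---|---|---|
| As written | 21/22 = 95.5% | 77.2, 99.9 |
| Reinfection excluded from mFAS/TRD=F | 21/21 = 100% | 83.9, 100 |

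The second lower limit is 0.025^(1/21) = 0.839. The estimate moves by 100 − 95.5 = 4.5 points and the lower limit by 83.9 − 77.2 = 6.7 points. The key FAS/M=F result is 21/22 under both rules.

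**4. How likely is a case?** The documents give no rate. As an assumption only, take 0.5 to 10 per 100 person-years applied to all 22 adolescents, with P(at least one) = 1 − exp(−expected).

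| Window | Person-years | Expected cases | P(at least one) |
|---|---|---|---|
| To FW12 | 22 × 12/52 = 5.08 | 0.025 to 0.508 | 2.5% to 39.8% |
| To FW24 | 22 × 24/52 = 10.15 | 0.051 to 1.015 | 5.0% to 63.8% |

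Only the first row bears on SVR12. A later case can affect the relapse rate, SVR24 and the RAS summary.

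**The case against.** The strongest reply is that little depends on this. The trial tests no hypothesis and its primary endpoints are pharmacokinetic. The key SVR12 analysis is FAS/M=F, where counting a reinfection as failure is conservative and would stay so. Only supportive, descriptive and exploratory results can move, and Section 10.6 already defers methods for exploratory objectives to the sSAP. All of that stands, and it is why the point ranks as a cheap improvement.

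The exposure argument also has limits. Criterion 14 removes much of the risk, and opiate substitution sits in Table 7 among medications less commonly used in children. Being on substitution is not evidence of continuing exposure. The risk is lowered but not removed: the criterion covers only clinically relevant abuse within 12 months that may interfere with the trial, and Section 3.2.1.1 also names tattoos and piercings.

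A reader might infer more than the documents support:

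- **That any viraemia after treatment is relapse.** The definition requires TND at end of treatment. A participant who was TD(u) then and later has quantifiable virus fits none of the four categories, although SVR12 is still failed if the virus is present at FW12.
- **That high-risk behaviour is the main route of infection.** It is ranked first only among non-vertical routes.
- **That a reinfection would necessarily yield a treatment-emergent RAS.** The description also requires selection during therapy, which a substitution acquired with a new strain does not meet. Testing further needs RNA above 1000 IU/mL, and the new strain must carry a RAS absent at baseline. The fault is the missing check, so the mislabel is a risk and not a certainty.
- **That correcting the rule restores 22/22.** Excluding the participant gives 21/21.

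Finally, N = 22 is not assured: Section 10.6.3 reports Mini and Expanded cohorts separately if their doses differ.

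**Conclusion.** The gap is real and one of definition. As written, a new-strain infection in a participant who was TND at end of treatment is reported as relapse and, if present by FW12, as failure in the supportive mFAS/TRD=F SVR12. Counting it as treatment-emergent resistance is possible under the conditions above.

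The effect in Step 3 assumes one case by FW12, 22 adolescents analysed together and no other failure. With no case there is no effect. How probable a case is rests wholly on an assumed rate. No sample-size or precision figure in the plan is wrong, and a reader should not conclude that the key efficacy estimate is compromised. Label: cheap improvement, low probability of effect.

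**What to change.** In Sections 5.4.2.1.1 and 10.6.3, or in the sSAP before any failure data are seen:

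- **Define reinfection.** Confirmed post-treatment viraemia is reinfection when genotype/subtype differs from baseline, or when the NS3/NS5A sequence does not cluster with the participant's own baseline sequence under a pre-set criterion.
- **Set the default.** Cases that cannot be sequenced, for example with HCV RNA not above 1000 IU/mL, remain relapse.
- **State the handling.** Keep reinfection as a failure in FAS/M=F and report it as its own row. Exclude it from mFAS/TRD=F as a non-virologic failure from the affected time point on, so that an SVR12 responder reinfected later stays a responder at SVR12. Leave it out of the treatment-emergent RAS summary.

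Timing matters because the trial is open-label: deciding after the fact that a failure was a reinfection would look self-serving.

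The cost is wording, a clustering criterion fixed in advance, and extending the phylogenetic analysis, now planned for genotype/subtype assignment, to the few failure samples. The NS3/4A and NS5A sequences it needs are already planned, subject to the 1000 IU/mL threshold.
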